11.6. Appendix 6: Premature Withdrawals & Handling of Missing Data

11.6.1. Premature Withdrawal

The reasons for subjects not completing the treatment period will be recorded as detailed in Section 4.5 of the protocol. Subjects who discontinue active participation in the study will no longer receive the randomized study medication. Immediately upon discontinuation from active participation in this study, these subjects should complete the early withdrawal assessments and return 4 weeks later for the follow-up assessments.

The reasons for subjects not completing the study will be recorded. Subjects who are withdrawn will not be replaced.

Per the protocol, insulin lispro may be re-introduced after Week 8 for subjects in the albiglutide treatment group, following a standardized, stepwise approach. Efficacy and safety assessments after the re-introduction of lispro will be included in the statistical analysis as is, without special handling.

11.6.2. Missing Date Imputation

In general, partial dates will be imputed as follows:

A partial event start date, partial start dates of prior and concomitant medications or partial diagnosis date will be assumed to be the earliest possible date consistent with the partial date.

- If year is missing, the year will be assumed to be the year part of informed consent date of that subject;
- If month is missing, the month will be assumed to be January;
- If day is missing, it will be assumed to be the first day of the month.
- In the case of a completely missing start date, the start date will be assumed to be prior to date of the first administration of study drug.

Partial event or medication stop dates will be assumed to be the latest possible date consistent with the partial date.

- If month is missing, it will be assumed to be December;
- If day is missing, it will be assumed to be the last day of the month.
- In the case of completely missing stop date, the stop date will be assumed to be after the date of the last study visit; the event or medication are considered as ongoing.

For AE date imputation this rule will be followed but will be more conservative in nature consistent with the therapy phase (see [Appendix 4: Treatment Periods](#) for details).

Since only the year of birth is recorded for subjects in this study, the age of the subjects for analysis purposes is calculated using June 30 of the birth year as the imputed subject birth date.

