6.9. Medical History

Subject data listings and summary tables will be provided for the following current and/or past conditions:

- cardiovascular medical history
- diabetes history
- medical/surgical procedure history
- gastrointestinal (GI) medical history

- nephropathy (including microalbuminuria) and kidney injury history
- diabetic retinopathy history
- cancer history
- pneumonia medical history
- skin medical conditions
- thyroid history, thyroid cancer history
- history benign thyroid conditions
- thyroid cancer family history
- pancreatitis family history
- pancreatic cancer family history
- other medical history

The number and percentage of subjects with current and/or past cardiovascular medical history will be reported by treatment group. Also, the number and percentage of subjects with current and/or past diabetes history will be tabulated by treatment group. A summary of duration of diabetes disease history in years will be provided. The duration of diabetes disease history is calculated as the years lapsed between screening visit date and T2DM diagnosis date.

The number and percentages of subjects with current and/or past medical/surgical procedure history, gastrointestinal (GI) medical history, nephropathy (including microalbuminuria) and kidney injury history, diabetic retinopathy history, cancer history, pneumonia medical history, skin medical conditions, thyroid history, thyroid cancer history, history benign thyroid conditions, thyroid cancer family history, pancreatitis family history, pancreatic cancer family history and other medical history will be presented in a similar manner as described for cardiovascular medical history.

In addition, by subject listings of medical and family history status and all the medical conditions listed above will be provided.

All summaries will be performed using the safety population. In the case of scarce data for a medical history and summary is not necessary, only a listing will be provided.

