11.4. Appendix 4: Treatment Periods

For classifying AEs (including hypoglycemic events), the therapy periods will be defined as:

- **Pre-therapy:** The onset date of the AE is before the start date of randomized study medication. If the onset date of the AE is on the start date of randomized study medication, the AE will be considered as on-therapy.
- **On-therapy:** The onset date of the AE is on or after the start date of randomized study medication, and within last dose date plus 25 days in the albiglutide arm or within the last dose date in the lispro arm.
- **Post-therapy:** The onset date of the AE is more than 25 days after the last dose date in the albiglutide arm or after the last dose date in the lispro arm.

For immunogenicity data and other safety parameters that are assessed prior to administration of randomized study medication on dosing days, the therapy periods will be defined as:

- **Pre-therapy:** The assessment date is on or before the start date of randomized study medication.
- **On-therapy:** The assessment date is after the start date of randomized study medication, and within last dose date plus 25 days in the albiglutide arm or within the last dose date in the lispro arm.
- **Post-therapy:** The assessment date is more than 25 days after the last dose date in the albiglutide arm or after the last dose date in the lispro arm.

For an AE with an incomplete start date where the year and month are present while the day is missing, or where the year is present while both month and day are missing, the date is imputed in a dynamic way consistent with the partial date information so that the resulting AE therapy period assignment based on the imputed date is the most conservative possible, where the order from the most to the least conservative is: on-therapy phase > post-therapy phase > pre-therapy. Note that if the AE stop date is present, the imputed start date will always be on or prior to the stop date.

For the subjects in the insulin lispro + insulin glargine arm, the first drug dispense date recorded on eCRF after randomization is considered the starting date of treatment period. For the last dose date, it will be derived based on the last visit date. The last dose date will be Week 30 follow-up visit date for subject who completed the study, or the 4-week follow-up visit/end of study visit date for subjects who withdrew early.

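### SAP 11.6.2 sends a year-missing diabetes diagnosis or insulin start to the consent year, and the conservative adverse-event rule in SAP 11.4 stops short of events with no year or no start date

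*SAP*

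**What the plan says.** SAP 11.6.2 gives one general rule for partial event start dates, medication start dates and diagnosis dates. The imputed date "will be assumed to be the earliest possible date consistent with the partial date". The bullets that carry this out are:

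- Missing year: "If year is missing, the year will be assumed to be the year part of informed consent date of that subject".
- Missing month: "If month is missing, the month will be assumed to be January". A missing day becomes the first of the month.
- Completely missing start date: "the start date will be assumed to be prior to date of the first administration of study drug". No calendar date is assigned.

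For adverse events the section adds: "For AE date imputation this rule will be followed but will be more conservative in nature consistent with the therapy phase", and refers to Appendix 4.

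Appendix 4 (SAP 11.4) imputes an incomplete adverse-event start so that the therapy period is the most conservative one the known parts allow, "where the order from the most to the least conservative is: on-therapy phase > post-therapy phase > pre-therapy". It names two cases: only the day missing, "or where the year is present while both month and day are missing". If a stop date is known, the imputed start may not fall after it.

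The diagnosis date feeds diabetes duration in SAP 6.9: "The duration of diabetes disease history is calculated as the years lapsed between screening visit date and T2DM diagnosis date". Duration (under 8, 8 to 13, over 13 years) is a subgroup of the primary endpoint in SAP 11.9.2. Duration and time on insulin are both candidate risk factors in the exploratory lispro re-introduction analysis of SAP 8.1.2.1.

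**The concern.** There are two defects.

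**Diagnosis and insulin-start dates.** These events lie before study entry, so the consent year is the latest year they can have. The year bullet therefore does the opposite of the principle it is meant to implement, and nothing elsewhere in the SAP overrides it for these dates. A person already on basal-bolus insulin, and possibly diabetic for decades, would be recorded as newly diagnosed or as diagnosed after consent. The error always shortens the disease history. It puts the subject in the wrong duration subgroup and distorts two predictors in the re-introduction analysis.

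**Adverse events.** SAP 11.6.2 promises a more conservative treatment, but the only place that spells it out, SAP 11.4, applies only when the year is known. An event with no start date, or with only the year missing, has no rule there. Read literally, it falls back to the general bullets. A wholly undated event then becomes pre-therapy, the least conservative class in SAP 11.4's own ranking. It would leave the on-therapy summaries and the treatment-emergent summaries, which are defined as on- plus post-therapy (SAP 8.3.2.2). The same period classes apply to hypoglycemic events.

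**Working it through.** The plan states no figure on this point, so there is nothing to reproduce. The rules can be applied by date arithmetic. Assumptions, where the documents give no value: consent dates spread evenly over a 365-day year; consent on the screening date; first dose 42 days later (screening at Week -6); albiglutide on-therapy period of 201 days (last dose at Week 25 is Day 25 × 7 + 1 = 176, plus 25 days).

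**1. Diagnosis date, month known, year and day missing.** The imputed date is the first of that month in the consent year.

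- Longest duration: consent 31 December, imputed 1 January, 364/365.25 = 0.997 years.
- Shortest: consent 1 January, imputed 1 December, -334/365.25 = -0.91 years.
- Over all combinations of consent day and month, about 46% put the diagnosis after consent, giving a negative duration.

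Every value is below 8 years, so every such subject lands in the shortest-duration subgroup whatever the true history.

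**2. Diagnosis date with neither year nor month, if the year and month bullets are applied.** The imputed date is 1 January of the consent year. Duration runs from 0 to 0.997 years, mean 0.50. If instead the completely-missing bullet governs, no date is assigned and duration is undefined. For a wholly unknown diagnosis date the SAP does not say which applies.

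**3. Insulin start imputed to 1 January of the consent year.** The gap to first dose runs from 42/365.25 = 0.11 to (364 + 42)/365.25 = 1.11 years. SAP 8.1.2.1 uses the earliest start among prior insulin records, so this value decides the result only when no other insulin record has an earlier known start.

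**4. Adverse event, year known.** SAP 11.4 applies and assigns on-therapy wherever the known parts allow. There is no problem here.

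**5. Adverse event, day and month known, year missing.** The fallback is the consent year. A true on-therapy onset in the consent year is placed correctly. An onset in the following calendar year is moved back a year and lands before first dose. With onset spread evenly over the 201 days (offset 0 to 200, mean 100), the share falling in the next calendar year is (42 + 100)/365 = 0.389, about 39%.

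**6. Adverse event, start date completely missing.** All become pre-therapy on the literal text. That is also the less likely class. Protocol 6.3.11 collects adverse events from the start of Standardization (about Week -4) to follow-up (Week 30), 34 weeks, of which 4 precede treatment: 4/34 = 12%. With evenly spread onset, about 88% of undated events would have started on or after first dose.

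**7. Comparison with the SAP's other adverse-event defaults.** A missing relationship is counted as related (SAP 8.3.2.3) and a missing intensity as severe (SAP 8.3.2.4). The fallback for a missing date runs the other way.

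**The case against.** Several points on the other side stand.

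- A reader might infer that any unknown diagnosis date gives near-zero duration. The documents do not support that. A completely missing start date has its own bullet, which assigns no calendar date. The clear error is confined to dates with some part known but no year, and that pattern should be uncommon for an old diagnosis.
- The consent year is not too late for events that begin on study. Collection starts after consent, so for those the consent year is the earliest possible one. The contradiction with the lead-in concerns diagnosis dates and medications started before the study.
- The sentence in SAP 11.6.2 promising more conservative handling of adverse events is not itself limited to known years. The defect is a gap in SAP 11.4, not a rule designed to remove events.
- A reader might infer that undated events disappear. They do not: pre-therapy events have Table 3.13, pre-therapy serious events have Table 3.41, and all adverse events are listed.
- A reader might infer that an imputed insulin start can break the entry criterion on prior insulin use. Eligibility is judged at Screening, not from imputed analysis dates.
- Frequent visits and calls, with data cleaning, should make wholly undated events rare.

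What remains is that the year bullet, when followed, gives a wrong value for a diagnosis or insulin start, and that a programmer working from the text has no instruction for an adverse event without a year except the one that moves it away from on-therapy.

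**Conclusion.** Wrong as written, with minor consequences. A year-missing diagnosis or insulin-start date yields a duration under about 1 year or a negative one. An adverse event with no start date defaults to pre-therapy, and one missing only the year can be placed before first dose. The 39% and 88% figures rest on the even-spread and timing assumptions above. The direction of the errors does not.

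The documents give no count of missing dates, so no share of misclassified subjects or events can be stated. The number is probably small. No effect on the primary or key secondary analyses is shown. The primary model has no duration term (SAP 7.1.1.1), and the weight and insulin-dose comparisons use neither diagnosis nor event dates. SAP 8.1.2.2 does not tie its hypoglycemia percentage to the therapy periods, so the documents do not show an effect there either. What is affected is one subgroup display without multiplicity adjustment, one exploratory risk-factor analysis, and the on-therapy and treatment-emergent safety counts.

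**What to change.** Two changes before database lock.

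- **SAP 11.6.2:** when the year of diabetes diagnosis is unknown, whether the date is partial or wholly missing, impute nothing. Leave duration missing, and leave the subject out of the duration subgroups and of any model using duration. Treat time on insulin the same way when the insulin-start year is unknown and no other insulin record gives a known earlier start.
- **SAP 11.4:** extend the existing most-conservative rule to adverse events with a missing year or a completely missing start date. Class them as on-therapy unless the stop date or the known part of the start date rules it out.

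The cost is about two lines of text. A few subjects drop out of the duration display, and a few events may be over-counted as on-therapy, a price SAP 11.4 already accepts for partial dates. The second change carries out the intent SAP 11.6.2 already states.

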11.6.3. Sensitivity Analysis on the Primary Efficacy Endpoint

Missing data are not explicitly imputed in the primary MMRM analysis; although there is an underlying assumption that data are missing at random, including those withdrawn for lack of efficacy. The MMRM method will produce an unbiased estimate of treatment effect under the missing at random (MAR) assumption.

The sensitivity of the results of analysis to the method of handling missing values will be investigated, especially if the number of missing values is substantial or if the characteristics of missing values differ between treatment groups.

11.6.3.1. Extent of Missing Primary Analysis Data Endpoint

Missing data is expected to arise mainly from subjects missing complete visits. The amount of missing data for those baseline covariates included in the statistical analysis is expected to be none or at worst minimal. If it should occur, that subject will effectively be lost to analysis. Missing data for HbA_{1c} between two non-missing visits will be considered missing at random (intermediate missing data).

In this study, subjects who withdraw from treatment will be withdrawn from the study. In the eCRF, the reason for treatment discontinuation and the reason for withdrawal from the study are collected separately. Whenever the HbA_{1c} value at Week 26 is missing (end of the study), the reason can be determined based on available data in these two locations. The reason for missing data can be classified as follows: safety, procedural (including withdrawal of consent), or lack of efficacy.

11.6.3.2. Reasons for Withdrawal

Reasons for withdrawal are assumed to fall into three broad categories:

- Procedural (i.e. lost to follow-up, investigator site closed, withdrew consent, protocol deviation, and investigator discretion that are not related to study treatment): In this case, it is expected that an assumption of missing at random (MAR) is appropriate for imputation of HbA_{1c} data after withdrawal.
- Safety (i.e. AE; subject reached protocol-defined stopping criteria; withdrew consent, protocol deviation, and investigator discretion that are related to study treatment): It is expected that, in most cases, any change in safety related to these reasons for withdrawal would have been captured prior to the subject withdrawing from the study. In Study GLP108486 (albiglutide versus lispro over background glargine), 5% of subjects in the albiglutide group and <1% in the lispro group had AEs leading to withdrawal of active treatment through Week 26. In the albiglutide group, the most common AE leading to withdrawal was injection site reaction (1.1%). Missing HbA_{1c} values after withdrawal due to safety concerns will be considered to possibly be missing not at random (MNAR).

- Lack of efficacy: In this treat-to-target study, a substantial number of cases of withdrawal due to lack of efficacy is not expected. Missing HbA_{1c} values after withdrawal due to lack of efficacy are considered to possibly be MNAR.

Sensitivity analyses will be performed for data missing due to safety concerns or due to lack of efficacy.

11.6.3.3. Handling of Missing Data

The impact of missing data will be explored, as outlined below, for the Full Analysis Population only.

Examination of Missing Data Patterns

To examine the nature of missing data, cohorts of subjects will be defined based on the scheduled assessments (HbA_{1c} change from Baseline) that were completed at Weeks 4, 5, 10, 18 and 26.

1. Subjects who have Week 4 assessment only
2. Subjects who have assessments up to and including Week 5 only
3. Subjects who have assessments up to and including Week 10 only
4. Subjects who have assessments up to and including Week 18 only
5. Subjects who have assessments up to and including Week 26.

The number and percentage of subjects on each treatment in the 5 cohorts defined here will be tabulated. Graphical methods will be used to examine changes from Baseline over time to assess the pattern of outcomes prior to withdrawal.

Sensitivity Analyses – Multiple Imputation

Sensitivity analyses using multiple imputation methods will be conducted. Firstly, missing data between two non-missing time points will be considered missing at random.

The following multiple imputation methods are proposed based on whether data are missing at random or not at random:

- All missing data assumed MAR: Imputation is based on means and variances-covariances from subjects in the same treatment group as the withdrawn subject and is comparable to MMRM. The main differences are that this approach uses separate covariance parameter estimation for each arm, and also separate regression parameters are estimated on baseline covariates within each arm. This more complex parameterization of the imputation model compared with the analysis model is valid. This approach will be used for all data missing post withdrawal. Here the estimand is one where after withdrawal all subjects progress in a similar way to those who remain in the trial. We expect the MMRM and this to give similar answers. If so, then it indicates any difference between the primary MMRM analysis and multiple imputation sensitivity analysis is due to the assumed effect modification and the assumed rates of HbA_{1c} increase after withdrawal, rather than anything to do with going from an MMRM approach to a multiple imputation approach.
- Missing due to lack of efficacy or due to safety concerns using last mean carried forward (LMCF), which is MNAR (Carpenter and Kenward (2013)) (Step 2

below). The imputed values based on LMCF will be then updated with an added delta using a constant rate of increase in HbA_{1c} change from Baseline is experienced by subjects following withdrawal from the study for lack of efficacy or due to safety concerns (Step 3 below). The MAR approach will be used for missing data due to procedural reasons. Sensitivity analyses using the LMCF approach will be performed using the following rates of HbA_{1c} increase: 0%/month, 0.1%/month, and 0.2%/month to explore the potential impact as in a tipping-point analysis. For each treatment group, these 3 rates will be assumed, resulting in 9 scenarios. The resulting treatment differences and associated P-values for non-inferiority will be tabulated against the varying rates of HbA_{1c} increase. This estimand is one where those who withdraw for lack of efficacy or for safety concerns are assumed to revert to an unstable treatment regimen with an increasing rate of HbA_{1c}.

For each imputation data set, an analysis of variance will be carried using Week 26 data, both actual and imputed, using the same covariates as in the primary analysis. Contrasts of interest will be estimated and then combined across imputations using standard multiple imputation rules.

The details of implementing the multiple imputation assuming MAR and the multiple imputation using the LMCF approach are the following:

- Step 1: Multiple Imputation under MAR ($K=100$ times)
 - Run PROC MI for all subjects BY treatment group (specifying the options chain=multiple in the MCMC statement).
 - As a result 100 sets of mean vectors (μ) and variance-covariance matrices (Σ) for each treatment group are simulated from the posterior distribution.
 - Each of the above 100 simulated parameter sets leads to a separate imputed dataset, in which the missing values (\mathbf{Y}_2) for each subject are replaced by values drawn randomly from their conditional distribution given the observed values (\mathbf{Y}_1). This condition distribution ($\mathbf{Y}_2|\mathbf{Y}_1$) is multinomial with mean $\mu_2 + \Sigma_{21} \Sigma_{11}^{-1} (\mathbf{Y}_1 - \mu_1)$ and variance-covariance matrix $\Sigma_{22} - \Sigma_{21} \Sigma_{11}^{-1} \Sigma_{12}$. So, 100 imputed datasets are generated.
- Step 2: Multiple Imputation using LMCF ($K=100$ times)
 - For each imputed dataset from Step 1, update the imputed values (post-last observation) for only subjects who withdraw due to lack of efficacy and safety concern as follows:
 - For each subject per treatment group, if there are any imputed values after the last observation ($\mathbf{Y}_{p, \text{imp}}$), first split the simulated mean vector (μ) into three parts: μ_b (prior to last obs), μ_{last} (last obs) and μ_p (post last obs) and then update these imputed values as $\mathbf{Y}_{p, \text{imp}}^* = (\mathbf{Y}_{p, \text{imp}} - \mu_p + \mu_{\text{last}})$. Repeat for all subjects and for both treatment groups.
 - Repeat for the 100 imputed datasets from Step 1.
- Step 3: Multiple Imputation using added delta value ($K=100$ times)
 - Calculate delta value for each subject at each visit post-last observation

- Let γ_1 and γ_2 be the rates of HbA1c increase per month after the last observation for the Albiglutide and Insulin Lispro treatment group, respectively.
- Let τ be the length of time between visits. Also, consider 1 month=4 weeks and determine τ using the visit week values. For example, time between visits Week 16 and Week 20 is 4 weeks (i.e. 1 month) and time between visits Week 16 and Week 26 is 10 weeks (i.e. 10/4=2.5 months).
- For each subject and each visit post-last observation, a delta value will be derived according to the treatment group the subject was randomized to and time between the last observation visit and the present visit (τ). If the subject belongs to the Albiglutide treatment group, the delta value = $\gamma_1 \times \tau/4$; if the subject belongs to the Insulin Lispro treatment group, the delta value = $\gamma_2 \times \tau/4$.
- For each updated imputed dataset from Step 2 increase the imputed values post-last observation by the corresponding delta values (per subject per visit post-last observation).
- Repeat for the 100 imputed datasets from Step 2
- Step 4:
 - Perform Step 1 only for one scenario under MAR with 100 imputed datasets generated
 - Repeat Step 1, Step 2 and Step 3 for additional 9 scenarios using LMCF/delta method based on different rates of HbA1c increase for each treatment group
 - $\gamma_1=0/\text{month}, \gamma_2=0/\text{month}$
 - $\gamma_1=0/\text{month}, \gamma_2=0.1/\text{month}$
 - $\gamma_1=0/\text{month}, \gamma_2=0.2/\text{month}$
 - $\gamma_1=0.1/\text{month}, \gamma_2=0/\text{month}$
 - $\gamma_1=0.1/\text{month}, \gamma_2=0.1/\text{month}$
 - $\gamma_1=0.1/\text{month}, \gamma_2=0.2/\text{month}$
 - $\gamma_1=0.2/\text{month}, \gamma_2=0/\text{month}$
 - $\gamma_1=0.2/\text{month}, \gamma_2=0.1/\text{month}$
 - $\gamma_1=0.2/\text{month}, \gamma_2=0.2/\text{month}$
- Step 5: For each of the above 10 scenarios, apply ANCOVA analysis at Week 26 for each of the 100 imputed datasets and save the difference in LSmeans between treatment group and the associated standard error from each of the 100 analyses.
- Step 6: For each of the above 10 scenarios, combine the 100 set of analysis results using Rubin's rules (Rubin, 1987) via SAS PROC MIANALYZE. The treatment differences, confidence intervals and p-values will be estimated by MODELEFFECTS and STDERR statement. Use the degrees of freedom (EDF) you would have if the dataset were complete.

